2.5 Treatments

The study product is LF111, which consists of coated tablets containing 4.0 mg DRSP. One package includes 24 active (white) tablets followed by 4 placebo (green) tablets. The dose for each subject is one tablet per day. During each medication cycle, the subjects will take 24 active tablets (each containing 4.0 mg DRSP) followed by 4 placebo tablets.

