5.4 Exposure to IMP and Compliance

5.4.1 Exposure to IMP

Exposure data include:

- Date of the first IMP intake (subject's diary)
- Date of the last IMP intake
- Date of IMP dispensation
- Number of white tablets dispensed
- Number of green tablets dispensed
- Date of IMP collection
- Number of white tablets collected
- Number of green tablets collected
- Numbers of tablets taken (subject's diary)
- Date of IMP intake with time in hours and minutes (subject's diary)

Exposure data are derived from appropriate eCRF pages and diary. If the 1st regular IMP intake (variable PILDT in subject's diary) was not entered, but the first IMP intake (variable BPILDTC in subject's diary) was entered then the 1st regular IMP intake will be derived from BPILDTC by adding time "T00:00".

Derived variables:

Overall treatment duration will be calculated as follows:

Overall treatment duration

$$= \text{Date of the last IMP intake} - \text{Date of the first IMP intake} + 1.$$

Cumulative exposure will be categorized as:

- ≥ 28 days
- ≥ 84 days
- ≥ 168 days
- ≥ 252 days

Missing Entries of IMP Intake in Treatment Diary

Missing IMP intake entries will be classified as total number of missing entries and consecutive missing entries per respective cycle. Total and consecutive number of missing entries will be categorized as:

- Total missing entries over up to 13 cycles
 - 0-2 missing entries
 - 3-5 missing entries
 - 6-8 missing entries
 - 9 or more missing entries
- Total missing entries per separate cycle
 - 0 missing entries
 - 1 missing entries
 - 2 missing entries
 - 3 missing entries
 - 4 or more missing entries
- Active tablet free interval. Active tablet free interval is >48h tablet free interval during the second IMP intake till day 24 of each cycle or >144h interval between the last IMP intake and the first IMP intake in consecutive cycles. Tablet free interval calculation will not take into account cycle days 25-28.

Tables

No.	Name	Analysis set	Comments
Table 15.1.17.1.1	Exposure to Investigational Medicinal Product	Safety	Default summary statistics for the overall treatment duration in days will be presented. Default frequency tabulation for cumulative overall treatment duration will be displayed. Percentage will be based on the number of subjects in the SS. Data of centers 104 and 120 will be excluded.

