Table 15.1.18.1.1	Number of Subjects with at Least One Missing Entry of IMP Intake in Treatment Diary by Treatment Cycle and Overall	Safety	Numbers and percentages of subjects having at least one missing IMP intake will be presented. Number of missing IMP intakes will be presented by treatment cycle and overall. Percentage will be based on the number of subjects in respective cycle. Data of centers 104 and 120 will be excluded.
Table 15.1.19.1.1	Number of Subjects with Gaps between Two Active Tablet Intakes of More Than 48/144 Hours by Treatment Cycle and Overall	Safety	Numbers and percentages of subjects having >48h (or 144h for the 1 st IMP intake) active tablet free interval. Number of >48h (or 144h for the 1 st IMP intake) active tablet free interval will be presented by treatment cycle and overall. Percentage will be based on the number of subjects in respective cycle. Data of centers 104 and 120 will be excluded.

Listings

No.	Name	Analysis set	Comments
Listing 16.2.1.14	Drug Accountability	Enrolled	Dispensation and collection of IMP will be listed for the subjects from ES.

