Method failure pregnancy*	All on-drug pregnancies of women who used the IMP correctly. Pregnancies are to be excluded from the calculation if in medication cycles of conception or in the previous medication cycles depending on the date of conception: 
 - not all active tablets are taken (based on returned medication, recordings in the e-diary and non-compliance based on DRSP levels, if necessary) - there is an active tablet free interval between the previous medication cycle and the medication cycle of conception. Tablet free interval will be determined by record from treatment diary. - vomiting or diarrhea is documented - administration of prohibited prior or concomitant therapy as detailed in Section 10.7 of the Clinical Trial Protocol is documented
Exposure cycles	28-day cycles, where at least one treatment diary entry of IMP intake is available. In addition, a cycle will be an exposure cycle if the subject become pregnant during this cycle regardless this cycle was a 28-day cycle or not.
Evaluable cycle	Cycles are exposure cycles with intercourse without back-up contraceptive at least once per cycle based on electronic diary question 'Did you have sexual

	
intercourse since the beginning of the cycle?" and answered with: 'Yes I had sexual intercourse without additional contraception'.
 
Also, cycle is to be defined as evaluable if:
 
 - Subject became pregnant at the respective cycle regardless back-up contraception was used or not. - Cycle has missing answer about intercourse or answered "I had NO sexual intercourse at all" but subject became pregnant at the respective cycle. 
Cycle will not be defined as evaluable if subject did not become pregnant and:
 
 - The question was answered with 'Yes I had sexual intercourse with additional contraception'. - Cycles with NO intercourse. - Cycle has missing answer about intercourse.
Perfect cycle*	
Evaluable cycles which have no:
 
 - >48h tablet free interval during the second IMP intake till day 24 of each cycle or >144h interval between the last IMP intake and the first IMP intake in consecutive cycles. Tablet free interval calculation will not take into account cycle days 25-28. - 4 or more days with forgotten tablets intake during 1-24 cycle days. - Protocol deviations having effect on this cycle.

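### The perfect-cycle gap limits equal the gap left by one skipped active tablet, so logged clock time decides which one-skip, pregnancy-free cycles enter the method-failure Pearl Index denominator

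*SAP*

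**What the plan says.** SAP 2.5 sets the schedule: "The dose for each subject is one tablet per day", with 24 active tablets "followed by 4 placebo tablets". SAP 5.4.1 collects the "Date of IMP intake with time in hours and minutes" from the diary.

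SAP 5.5 defines a perfect cycle as an evaluable cycle that passes three further tests:
- no ">48h tablet free interval during the second IMP intake till day 24 of each cycle or >144h interval" between the last intake of one cycle and the first of the next, with the added rule that "Tablet free interval calculation will not take into account cycle days 25-28";
- no "4 or more days with forgotten tablets intake during 1-24 cycle days";
- no protocol deviation affecting the cycle.

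Both gap limits are strict inequalities. No tolerance, rounding or calendar-day rule is stated. SAP 5.4.1 repeats the limits for the active tablet free interval and reports them in Table 15.1.19.1.1, "Number of Subjects with Gaps between Two Active Tablet Intakes of More Than 48/144 Hours by Treatment Cycle and Overall". Listing DRM06 (SAP 3.3) also uses a 48-hour cut.

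Perfect cycles are the denominator of the method-failure Pearl Index (SAP 5.5.2) and the basis of the method-failure life tables. The numerator follows a different rule. Under SAP 2.2.2 and 5.5, a pregnancy is not a method failure if any active tablet was left untaken in the relevant cycle, and the note below the definitions table says that such a cycle cannot be perfect.

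**The concern.** A threshold meant to separate adherent from non-adherent cycles should lie between the values that the two kinds of cycle produce. Both limits here lie on the value produced by the commonest lapse, a single skip. If the tablet after the skip is logged one minute later in the day than the tablet before it, the cycle fails. If it is logged at the same time or earlier, the cycle passes this test. Two women with the same tablet-taking are classed differently by minutes that they entered themselves.

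This needs no missing data and arises in pregnancy-free cycles alone. Because conception cycles are judged by tablets taken, the numerator excludes every recorded skip while the denominator keeps a clock-dependent share of them. The resulting index corresponds neither to use with no missed active tablet nor to use within a stated tolerance.

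**Working it through.** **1. Nominal gaps.** Gap = days between successive active intakes × 24 h (SAP 2.5).

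| Situation | Within a cycle | Across the placebo days |
|---|---|---|
| On schedule | 24 h | Day 24 to Day 29: 5 × 24 = 120 h |
| One active tablet skipped | 2 × 24 = 48 h | Day 23 to Day 29, or Day 24 to Day 30: 6 × 24 = 144 h |
| Two consecutive skips | 3 × 24 = 72 h | 7 × 24 = 168 h |

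Both limits in SAP 5.5 equal the one-skip row. The 144 h column reads the gap as last active to first active tablet, as the title of Table 15.1.19.1.1 indicates. The relation 144 = 48 + 96, with 96 h for four placebo days, fits that reading.

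**2. Chance that a one-skip gap exceeds 48 h.** Assumptions: the skipped tablet is not made up, and intake times vary symmetrically about the usual time and are recorded to the minute. The documents give no timing SD, so it was ranged.

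| Assumed SD (minutes) | 5 | 15 | 60 | 180 |
|---|---|---|---|---|
| P(gap > 48 h, one skip) | 0.47 | 0.49 | 0.50 | 0.50 |

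With no skip the probability is about 0; with two consecutive skips it is about 1. Three isolated skips pass with probability about 0.5³ = 12.5%.

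**3. Effect on the denominator.** Let p be the skip rate per active tablet (assumed, skips independent, no make-up). Only the within-cycle limit is modelled. A skip on Day 1 or Day 24 creates no within-cycle gap, so 22 of the 24 days matter.
- Share of cycles with no skip: (1 − p)^24.
- Share passing as written: about (1 − p/2)^22, since each isolated skip passes half the time.
- Share passing a rule that tolerates isolated skips (no two consecutive skips, fewer than 4 in all): by simulation.

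| p | No skip | As written | Isolated skips tolerated |
|---|---|---|---|
| 1% | 0.786 | 0.896 | 0.998 |
| 2% | 0.616 | 0.802 | 0.991 |
| 4% | 0.375 | 0.641 | 0.957 |

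For a fixed number of pregnancies the Pearl Index varies inversely with the denominator:
- Relative to a no-skip denominator: 0.786/0.896 = 0.88; 0.616/0.802 = 0.77; 0.375/0.641 = 0.59.
- Relative to tolerating isolated skips: 0.998/0.896 = 1.11; 0.991/0.802 = 1.24; 0.957/0.641 = 1.5.

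A full simulation with timing SDs of 0.25, 1 and 3 h gives the same factors to within 0.01.

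**4. Late make-up.** A missed tablet taken late can keep the gap below 48 h. If a share m of misses is made up in that way, the one-miss failure rate is about 0.5 × (1 − m): 25% at m = 50% and 10% at m = 80%.

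**5. Conception cycles.** No probability enters. Under SAP 5.5 and its note, one recorded untaken active tablet excludes the pregnancy and its cycle whatever the clock time.

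**The case against.** **Intent and direction.** A reader might infer from the forgotten-tablet cap of four days that one to three misses are meant to be acceptable, so that the gap rule wrongly removes cycles and inflates the index. The documents do not support this. The tests are cumulative, so passing the cap does not excuse failing another test. The SAP's own account of correct use (2.2.2 and 5.5) requires all active tablets to have been taken. Measured against that standard, the rule keeps too many cycles and the index falls. The direction depends on the comparator, and both must be shown.

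**Make-up.** The protocol synopsis and SAP give no missed-tablet instruction, so the one-half figure holds only for skips that are not made up. Late make-up shrinks the effect, as step 4 shows. It does not move the limit off the nominal one-skip gap.

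**The 144 h limit.** The definition speaks of the last intake rather than the last active intake. If ignoring Days 25-28 meant subtracting 96 h, the on-schedule gap would be 24 h and it would take five skips to reach 144 h. The last-active-to-first-active reading fits better, but it remains a reading.

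**Table 15.1.19.1.1.** A reader might think that single skips vanish from reporting. They do not: missing intake entries are counted separately (SAP 5.4.1, Table 15.1.18.1.1), and the gap table reports what its title says.

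**Data review.** The review could remove some one-skip cycles as deviations, but SAP 3.3 states no missed-tablet criterion for doing so.

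**Conclusion.** The point stands for the denominator of the method-failure Pearl Index and for the method-failure life tables. Both are secondary; the primary Pearl Index uses evaluable cycles (SAP 5.5.1) and is not affected.

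The 48 h coincidence follows from the schedule alone. The 144 h coincidence depends on the last-active-to-first-active reading. About half of one-skip, pregnancy-free cycles fail if skips are not made up and timing is symmetric, almost regardless of the timing SD. A systematic shift in intake time after a miss would change the share, but clock time would still decide.

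The Pearl Index factors rest on assumed skip rates of 1% to 4%, independent skips, no make-up and a fixed pregnancy count. They show plausible size and do not predict this trial's result. It would go beyond the documents to say that the rule simply inflates the index, or that the SAP plainly tolerates isolated skips. What is established is that numerator and denominator use different adherence rules, and that the denominator's rule turns on minutes.

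**What to change.** - In SAP 5.4.1 and 5.5, replace the clock-hour limits with a count of active tablets not taken, derived from the diary and tablet records. Ignore placebo Days 25-28, and state how a late start of the next blister is counted, since a cycle begins with the first intake from its blister (SAP 4.6).
- Reconcile that count with the method-failure pregnancy definition, so that conception cycles and pregnancy-free cycles are judged by the same adherence rule.
- Report the method-failure Pearl Index twice: with only cycles having no skipped active tablet, and under the tolerance that the sponsor chooses and states.

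No particular tolerance is recommended here. Moving the hour limits to midway values would not be equivalent to a count: one skip followed by a tablet 13 h late gives 48 + 13 = 61 h with only one tablet missed. A limit based on consecutive skips, applied to conception cycles, would also admit pregnancies that the present definition excludes.

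The cost is SAP wording and a small programming change on data already collected. The perfect-cycle count will differ from the current draft outputs.

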3.3 Data Review

A data review meeting (DRM) will be held after database lock, prior to the final SAP and clinical database closure.

The following aims are defined for the DRM:

- to assign pregnancies to their category and cycle;
- to identify protocol deviations which may have impact on cycles;
- to assign subjects to each of the analysis sets;
- to check that there are no data issues that are outstanding or need resolution;
- to define complete and correct diary entry;
- to solve any outstanding issues in the SAP.

Appropriate trial team, including a physician, will review certain potential protocol deviations and will review relevant information regarding those deviations to determine whether each of them have an impact on a perfect cycle. Protocol deviations will be not categorized into major and minor rather they will be categorized according to their impact to the perfect medication cycle.

Inclusion criterion related deviations will be classified as follows:

Inclusion criteria (At Visit 1 (Screening) and at Visit 1b (Medication Dispensation), subjects must meet ALL of the following criteria)	Impact on the cycle	DRM listing no.

1. Sexually active, postmenarcheal and premenopausal female subjects at risk of pregnancy with no upper age limit.
 
Since Protocol Final Version 4.0: Sexually active, postmenarcheal and premenopausal female subjects at risk of pregnancy including breastfeeding women with no upper age limit.
	Case by case decision	IN01, IN02

2. Female subjects at risk of pregnancy, between the ages of 15 and 17 (inclusive) provided that
 
 • Applicable national, state and local laws allow subjects in this age group to consent to receive contraceptive services, • All applicable laws and regulations regarding the informed consent of the subjects to participate in clinical trials are observed, and • Subjects in this age group will also be encouraged to consistently and correctly use male condoms with every event of sexual intercourse. 
Since Protocol Final Version 4.0: Female subjects at risk of pregnancy, between the ages of 15 and 17 (inclusive) provided that
 
 • Applicable national, state and local laws allow subjects in this age group to consent/assent to receive contraceptive services, and 	All cycles	IN03

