* Method failure pregnancies will be only those which occurred during the perfect cycles, e.g., if pregnancy will contradict method failure definition then the cycle in which pregnancy occurred could not be called perfect cycle and vice versa.

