5.5.2 Secondary Efficacy Analysis

Secondary Efficacy Analysis will be based on non-breastfeeding women. Also, analysis will be performed in BMI subgroups.

Overall PI

Overall PI will be calculated based on exposure cycles for all women, aged ≤ 35 years and aged > 35 years:

$$PI \text{ (exposure cycles)} = \frac{\sum \text{on-drug pregnancy} \in \{\text{exposure cycles}\}}{\#\{\text{exposure cycles}\}} \times 1300.$$

Respective two-sided 95% CI for overall PI will be calculated according to formula in Section 5.5.

PI for method failures

PI for method failures will be calculated based on perfect cycles for all women, aged ≤ 35 years and aged > 35 years. Number of pregnancies will be calculated according to method failure definition:

$$PI (method failure) = \frac{\sum \text{method failure pregnancy} \in \{\text{perfect cycles}\}}{\#\{\text{perfect cycles}\}} \times 1300.$$

Respective two-sided 95% CI for PI for method failures will be calculated according to formula in Section 5.5.

Evaluable cycles PI

Evaluable cycles PI will be calculated based on evaluable cycles for all women and women aged > 35 years:

$$PI (\text{evaluable cycles}) = \frac{\sum \text{on-drug pregnancy} \in \{\text{evaluable cycles}\}}{\#\{\text{evaluable cycles}\}} \times 1300.$$

Respective two-sided 95% CI for PI based on evaluable cycles will be calculated according to formula in Section 5.5.

Life table analysis for pregnancy rate

Method failure life table analysis and life table analysis on evaluable cycles will be performed in all women, women aged ≤ 35 and > 35 years in order to have the pregnancy rate at each cycle and cumulative pregnancy rates for 6 and 13 cycles.

Cumulative pregnancy rate will be calculated by using the **PROC LIFETEST** procedure:

```
PROC LIFETEST DATA=<data set> METHOD=KM OUTSURV=CL CONFTYPE=LOG;
      TIME <time variable>*<censorship flag>(1);
      RUN;
```

The Kaplan-Meier method will be used to estimate the cumulative pregnancy ratio. Logarithmic transformation will be used for 95% CI of the pregnancy rate. The period from the start of treatment until the pregnancy will be the time variable in this analysis. Subjects who did not become pregnant will be censored at their time of the last intake of IMP.

Tables

No.	Name	Analysis set	Comments

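### The method-failure Pearl Index drops a pregnancy for one missed active tablet but can keep a non-pregnant cycle with isolated misses, a mismatch that by itself can only lower the index

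*SAP*

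**What the plan says.** SAP Section 5.5.2 sets the denominator: "PI for method failures will be calculated based on perfect cycles for all women", and likewise for the two age groups. The numerator is the method-failure pregnancies falling in those cycles.

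The definitions table in Section 5.5 gives the two adherence rules.

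- **Pregnancy.** It is excluded if, in the cycle of conception or in previous cycles (depending on the conception date), "not all active tablets are taken (based on returned medication, recordings in the e-diary and non-compliance based on DRSP levels, if necessary". Tablet-free intervals between cycles, vomiting or diarrhoea, and prohibited therapy also exclude it.
- **Perfect cycle.** This is an evaluable cycle with none of three features: a ">48h tablet free interval during the second IMP intake till day 24 of each cycle or >144h interval between the last IMP intake" of one cycle and the first of the next; "4 or more days with forgotten tablets intake during 1-24 cycle days"; or "Protocol deviations having effect on this cycle".

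A footnote links the two: "if pregnancy will contradict method failure definition then the cycle in which pregnancy occurred could not be called perfect cycle and vice versa". Section 3.3 has the trial team "review relevant information regarding those deviations to determine whether each of them have an impact on a perfect cycle". Section 2.5 gives the regimen as "24 active tablets (each containing 4.0 mg DRSP) followed by 4 placebo tablets". Section 2.2.2 says the method-failure rates are meant to cover only cycles of correct use.

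**The concern.** The two halves of the ratio use different adherence thresholds. One missed active tablet is enough to remove a pregnancy. A limit of four forgotten days has meaning only if one to three can be tolerated in a cycle without a pregnancy. A cycle with a tolerated miss adds to the denominator, yet a conception in it would be struck from the numerator.

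Pregnancies are also checked against returned tablets, drug levels and earlier cycles. The perfect-cycle rule does not apply these checks to other cycles.

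At stake is the figure a reader takes as the failure rate under correct use. The method-failure life tables also rest on perfect cycles and share the problem.

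**Working it through.** **Plan's own figure.** The plan states no expected method-failure PI and no missed-tablet rate. Its only planning figure, 920 women for 5000 evaluable cycles (Section 2.6), does not enter here.

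**Can a cycle with a miss stay perfect?** Consecutive active tablets are normally 24 h apart. From day 24 to day 1 of the next cycle is (29-24) x 24 = 120 h. One miss that is never made up gives 48 h within a cycle, or (29-23) x 24 = 144 h across cycles if day 24 is missed (likewise if day 1 is missed). Neither exceeds its limit at an unchanged clock time, and one forgotten day is fewer than four. Section 5.4.1 records intake in hours and minutes, so a later next intake does break the limit. Two consecutive misses give about 72 h and fail. If intake times vary symmetrically, about 0.52 of cycles with one miss stay perfect, about 0.25 with two and about 0.1 with three.

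**Direction of this component.** Let C0 be cycles with no miss, C1 non-pregnant cycles with tolerated misses, P0 pregnancies with no miss, and P1 pregnancies in cycles with tolerated misses.

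- SAP: 1300 x P0 / (C0 + C1)
- Strict rule on both sides: 1300 x P0 / C0
- Lenient rule on both sides: 1300 x (P0 + P1) / (C0 + C1 + P1)

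SAP divided by strict is C0 / (C0 + C1) = 1 - f, where f = C1 / (C0 + C1), so it is never above 1. The lenient PI is never below the SAP PI, because adding P1 to both parts of a proportion cannot reduce it. In 200,000 random combinations of the four counts, the SAP PI never exceeded either consistent version.

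**Size, on assumed inputs.** I simulated 13 cycles per woman with intake times varying by an SD of 1 h and applied the 48 h, 144 h and four-day limits. The miss rates are assumptions. The clustered row covers two models: a beta-distributed rate per woman (concentration 10 or 20), or a 0.3 or 0.5 chance of a miss following a miss.

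| Daily miss rate | 0.5% | 1% | 2% | 3% |
|---|---|---|---|---|
| f: independent, one rate for all women, never made up | 6% | 12% | 22% | 31% |
| f: clustered by woman or in runs, never made up | 2-3% | 4-7% | 8-13% | 11-19% |
| f: independent, 50% made up and counted as taken | 3% | 6% | 12% | 17% |
| f: independent, 80% made up and counted as taken | 1% | 2% | 5% | 7% |

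In the first row, a strict-rule PI of 2.0 would be reported as 2.0 x (1-f) = 1.9, 1.8, 1.6 and 1.4.

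**Effect of the strict rule.** With pregnancies unchanged, the PI and both confidence limits scale by 1/(1-f), from 1/0.99 = 1.01 to 1/0.69 = 1.45. For an assumed 6 method-failure pregnancies in 4000 perfect cycles, the PI is 1300 x 6/4000 = 1.95 (exact Poisson 95% CI 0.72-4.24). At f = 6% (3760 cycles) it is 2.07 (0.76-4.52), at 22% (3120 cycles) 2.50 (0.92-5.44), and at 31% (2760 cycles) 2.83 (1.04-6.15).

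**The case against.** **The footnote.** It might seem to align the rules, but it acts only on the cycle in which a pregnancy occurred. Non-pregnant cycles with the same misses stay in the denominator.

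**The data review.** It could remove such cycles as deviations, and if it removed all of them this mismatch would vanish. That stands as a possibility. Section 3.3 states no one-tablet rule, however, and its listing of intake gaps (DRM06) uses the same 48-hour threshold. DRM05, DRM08, DRM11 and DRM14 could help to find misses but set no threshold.

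**Net direction.** A reader might infer that the reported PI as a whole must be too low. The documents do not support that. Section 5.5 also keeps a cycle with back-up use, no intercourse or no answer about intercourse only if a pregnancy occurred, and likewise a cycle that was not 28 days long. Perfect cycles are drawn from these, so those rules push the same PI up.

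**Size.** The 6 to 31% row depends on independent misses at one rate for all women. Clustering roughly halves it or more, and make-up intakes lower it further. Only the protocol synopsis is available, so any instruction on late tablets is not visible.

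**Importance.** The endpoint is secondary and descriptive. Tables 15.1.7.1.1, 15.1.7.1.2 and 15.1.18.1.1 help a reader gauge the mismatch, but they do not correct the PI.

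**Conclusion.** The mismatch is in the current text, and its own direction follows from the algebra: it lowers the method-failure PI or leaves it unchanged. Neither the net direction of the PI nor the size of the effect is fixed by the documents. Across the assumed scenarios the strict rule would raise the PI and its limits by a factor of about 1.01 to 1.45, and the upper end needs a 3% daily miss rate, independence and no make-up. The method-failure life tables are affected in the same way; the primary evaluable-cycle PI and the overall PI are not. The rule should be corrected, because the change is cheap and the endpoint claims to describe correct use.

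**What to change.** In the Section 5.5 definitions and footnote, define one diary-based adherence flag per cycle, set without regard to pregnancy: every active tablet on days 1-24 recorded as taken, with a statement of whether a late make-up counts. Apply it to pregnant and non-pregnant cycles alike in the main method-failure PI, and use the same cycles in the method-failure life tables. The per-cycle missing-entry counts, tablets-taken field and intake times in Section 5.4.1 already supply the data.

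Add two sensitivity analyses:

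1. The 48 h, 144 h and four-day rule applied to both pregnancies and cycles.
2. The PI without pregnancies that fail only on returned-tablet, drug-level or earlier-cycle evidence. These stay in the main PI, because that evidence is not applied to other cycles. Give their number, for example in Table 15.1.7.1.1.

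The cost is SAP wording, one re-derived flag and two extra PIs. There will be fewer perfect cycles, a wider interval and a slightly less favourable PI. Some correct-use cycles will be lost where a tablet was taken but not recorded. Extending the earlier-cycle check to all cycles is not proposed: with independent misses never made up, it would leave only about 84, 71, 51 and 36% of the SAP's perfect cycles at the four assumed rates.
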